3.2.6.3 Loss to Follow-up

If a patient is lost to follow-up, the following information will be recorded:

- 1) date of last contact with patient
- 2) reasons for patient's unavailability: withdrawal, moved away, unreachable, and so forth
- 3) summary of attempts to contact patient
- 4) name and address of any physician who is following the patient

4.0 Risk/Benefit Assessment

The device is an implantable endoprosthesis intended to prevent aneurysm rupture. The hazards associated can be categorized as material-related, insertion related, and performance related. The consequent risks to the patient depend on the incidence and effects of each hazard, which have been explored in a large number of experimental and clinical insertions^{1,2,10}. These risks of endovascular aneurysm repair must be weighed against the risks associated with the current alternative forms of management.

4.1.0 Material-related Hazards

Material-related hazards include the lack of sterility, toxicity, and biodegradation of the device. The device will be packaged and sterilized by exposure to ethylene oxide (see appendix H). The stent-grafts will be opened in the operating room under the same conditions of sterility used for routine surgical procedures. The stents are made from T-304 stainless steel and there are no likely biocompatibility issues related to the stent. The graft material is twill woven from Micrel polyester yarn by Vasutec (Glasgow, UK). A gel-coated version of this fabric is approved for use as an arterial substitute in conventional surgery.

4.1.1 Deployment-related Hazards

The complications considered to be insertion-related hazards are those that occur during the insertion procedure. Previous clinical experience has provided extensive information on the incidence, avoidance, treatment, and consequences of many of these hazards^{1,2,9,10}.

4.1.1.1 Failure to traverse the iliac arteries

There have been no cases in which the delivery system designed in Perth could not be inserted through the iliac arteries. This is likely due to the relatively long tapered shape, and stiffness of the central carrier. The gradient stiffness of the nose of the device greatly facilitates insertion through tortuous iliacs. The soft, flexible end of the tip follows a guidewire around almost any bend, and in so doing, exerts force on the next segment of the tip to pass into the bend in the artery. This segment is less flexible, but with the help of the

preceding segment, it too can bend. This effect is repeated as the rest of the tip passes through the bend, with the segments becoming progressively more stiff. Eventually, the iliac artery is sufficiently straight to allow the remainder of the central carrier and sheath to pass. The effect of the central carrier stiffness is somewhat counter intuitive. The stiffer central carrier of the Perth system actually facilitates insertion through the tortuous iliac artery by preventing kinking of the sheath.

4.1.1.2 Stent-graft occlusion of the renal arteries

There has never been a case in which the renal arteries were excluded by the proximal end of this stent-graft design. The ability to optimize the graft position following deployment nearly always prevents inadvertent renal artery occlusion. (See Appendix B – Proximal fixation)

4.1.1.3 Proximal stent implanted below the neck of the aneurysm

There has never been a case in which the proximal end of the stent-graft was deployed within the aneurysm sac, likely for the same reasons listed in section 4.1.1.2. Were this to occur, a second stent-graft system could be easily deployed in the appropriate position.

4.1.1.4 Distal stent implanted too high

The modular design of this system allows one to place distal extensions sequentially, thus achieving any desired length. Re-instrumentation of the original stent-graft is quite simple.

4.1.1.5 Early endoleak

In the absence of stent-graft malposition, endoleaks can occur as a result of angulation of the stent relative to the implantation site. This occurs more commonly in the setting of a tortuous aorta. This phenomenon accounts for the 9 percent incidence of endoleaks noted in the preliminary work done with this device². The problem can be avoided by excluding any patient with a very tortuous aorta, or treated by re-orienting the stent following implantation with a cardiac valvuloplasty balloon. The balloon-driven “seating” is now part of the stent-graft implantation protocol.

4.1.1.6 Failure to deploy the stent-graft

The most difficult aspect of modular stent-graft deployment is often catheterization of the short limb. Failure of this step was responsible for the reported instances of failed stent-graft deployment, which occurred in 3 percent of the cases in Perth². All of these cases were among the early experiences of the investigators. Subsequently, a variety of maneuvers have been developed to eliminate this problem. Firstly, the delayed deployment of the proximal (supra-renal) stent permits one to access the short limb while maintaining the capability to reorient the main stent-graft body. Secondly, the long trunk of the stent-graft brings the orifice of the short limb close to the contralateral common iliac artery. Finally, if one is still unable to obtain access to the main stent-graft body through the short limb using the brachial or contralateral femoral arteries, the device can be converted into an aorto-monoiliac device quite easily.

4.1.1.7 Embolism

There have been 5 cases of peripheral embolism using this system. No cases of embolization produced limb-threatening ischemia. One risk factor appears to be the presence of a thrombus lining within the neck of the aneurysm at the proximal implantation site. Numerous investigators have had similar experiences.^{1,3,9} It seems prudent to exclude such patients from consideration for endovascular repair.

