2.0 Characteristics of the Research Population

- 1) Number of subjects. A total of 300 high risk patients will be enrolled in this study. The study will be conducted at the Cleveland Clinic Foundation. Enrollment will be on a rolling basis.
- 2) Gender of subjects. Gender is not an issue in this study. Enrollment will occur on a rolling basis regardless of gender.
- 3) Age of subjects. Subjects must be over 18 years of age. There is no maximum age however, patients must have an approximated life expectancy greater than 2 years.
- 4) Racial and ethnic origin. Racial and ethnic origin is not an issue in this study.
- 5) Inclusion criteria

General:

- a) the aneurysm is 5 cm or larger, or with a high risk of rupture due to its shape, history of growth, symptoms, or the presence of a large (>3.5 cm) iliac aneurysm
- b) anticipated mortality greater than 10 percent with conventional surgery*
- c) life expectancy greater than 2 years
- d) suitable arterial anatomy
- e) absence of systemic disease or allergy that precludes an endovascular repair
- f) capable of giving informed consent and willingness to comply with the follow-up schedule

* The risk of death following conventional operation (called “anesthetic risk”, although this is more closely related to the effects of surgery) will be determined primarily by the extent of co-morbid conditions, particularly cardiopulmonary disease. Clinical assessment will be determined in concert with medical and anesthesiology consultants when needed. Many factors weigh into the determination of operative risks. There are a wide variety of methods for attempting to quantify the relative effects of each risk factor however this has been done without reproducibility. In addition to the anesthetic risk, this analysis takes into account other risk factors for open surgical repair, such as retroperitoneal fibrosis, inflammatory bowel disease, prior radiation therapy, intestinal fistulae, and prior surgical procedures, all of which may complicate conventional surgical repair.

Anatomic:

- a) proximal neck > 10mm in length, \leq 32mm in diameter, and angulated no more than 80 degrees relative to the long axis of the aneurysm
- b) iliac artery diameter > 7mm (following balloon angioplasty or stenting if necessary)
- c) no signs that the inferior mesenteric artery is indispensable. These include angiographic visualization of a large IMA, filling of SMA via collaterals, or significant stenoses of the celiac or SMA.

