3.0 Methods and Procedures

3.1.0 Study Design

This study will be a prospective, non-randomized evaluation of endovascular aneurysm repair in high-risk patients.

Patients will be selected based upon the following criteria:

- Patients will be considered high risk if they meet any of the “General Inclusion Criteria”
- Patients will be considered anatomically suitable if they fulfill all of the appropriate “Anatomic Inclusion Criteria”

Patients must meet both the general and anatomic criteria to be enrolled in the study. General inclusion criteria will be assessed during the initial patient evaluation by conducting a history and physical examination. Anatomic criteria will be assessed using a variety of imaging techniques that are routinely performed during the evaluation of abdominal aortic aneurysms (see appendix A: Imaging Techniques Summary). The choice of axial imaging technique will be left up to the referral physician provided that the imaging protocol utilized is adequate for complete preoperative planning as defined in Appendix 1. Angiography and intravascular ultrasound will be performed selectively as is currently done prior to infrarenal abdominal aneurysm repair.

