3.1.2 Exclusion Criteria

- a) pregnancy
- b) history of anaphylactic reaction to contrast material with an inability to properly prophylax the patient appropriately
- c) allergy to stainless steel or polyester
- d) unwilling to comply with the follow-up schedule
- e) serious or systemic groin infection
- f) coagulopathy, other than coumadin therapy
- g) inability to give informed consent

3.1.3 *Anatomic Criteria*

- a) proximal neck > 10mm in length, <= 32mm in diameter, and angulated no more than 80 degrees relative to the long axis of the aneurysm
- b) iliac artery diameter > 7mm (following balloon angioplasty or stenting if necessary) and < 20mm
- c) no signs that the inferior mesenteric artery is indispensable. These include angiographic visualization of a large IMA, filling of SMA via collaterals, or significant stenoses of the celiac or SMA.
- d) iliac artery angulation < 90 degrees. In the presence of significant calcifications, the angle should be less than 60 degrees.
- e) for a straight aorto-aortic prosthesis, the distal neck (normal aorta between the aneurysm and iliac bifurcation) must be greater than 15mm in length, and less than 26mm in diameter.
- f) for a bifurcated aorto-biiliac prosthesis, the iliac implantation sites must be less than 2 cm in diameter and greater than 2 cm in length.

3.1.4 *Stent-graft sizing*

Grafts are currently custom made for each patient based on the findings from preoperative radiologic studies, including computerized tomography, magnetic resonance imaging, and conventional angiography. See appendix A for a detailed protocol of the imaging studies to be obtained.

3.1.4.1 **Stent-graft diameter**

The diameter of the graft is intended to be 10 to 15 percent (usually 3-4 mm) larger than the proximal implantation site (see appendix B). The attachment site for distal implantation is oversized by 5 to 10 percent (see appendix C). The assumption being that a small amount of graft redundancy would be inconsequential, whereas, as small deficiency in the diameter of the graft would result in either endoleakage or graft migration.

Straight grafts (aorto-aortic) are of uniform diameter. The larger of the two implantation sites determines the diameter of the graft. Aorto-iliac grafts (uni-iliac and bifurcated devices) have different proximal and distal diameters. Additionally, bifurcated devices may have differently sized segments at the ends of their right and left limbs.

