4.1.2.1 Proximal stent migration

This complication was seen in approximately 4% of the series described by the Perth group however, all occurred early in their experience. A retrospective analysis has improved our ability to predict which patients will suffer from migration. Looking specifically at the Perth experience, two migrations occurred in patients with an aortic implantation site measuring greater than 28 mm when an undersized stent-graft system was utilized. The third case occurred in a thrombus-lined neck, while the fourth case involved a conically shaped neck.

In addition to the necessary changes in the patient selection criteria, some changes were made to the stent-graft design and implantation methods. The proximal stent is now routinely placed in a supra-renal position. The healthier aortic wall affords better barb penetration and is more resistant to later dilation.

Appendix B contains detailed information regarding the benefits and safety of using supra-renal fixation device and other methods of ensuring aortic attachment.

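### Section 4.1.1.7 advises against treating thrombus-lined necks, but no eligibility criterion mentions thrombus, so the listed rules admit these patients

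*Combined protocol and SAP*

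**What the plan says.** On embolism, section 4.1.1.7 reports: "There have been 5 cases of peripheral embolism using this system". It adds that none threatened a limb, and goes on: "One risk factor appears to be the presence of a thrombus lining within the neck of the aneurysm at the proximal implantation site". It notes that other investigators have seen the same, and then gives its advice: "It seems prudent to exclude such patients from consideration for endovascular repair".

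On migration, section 4.1.2.1 goes through four Perth cases. Two were in wide necks with an undersized graft. Of the others it says: "The third case occurred in a thrombus-lined neck, while the fourth case involved a conically shaped neck". The next paragraph begins: "In addition to the necessary changes in the patient selection criteria, some changes were made to the stent-graft design and implantation methods".

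The neck criterion appears twice. In 3.1.3(a) it reads: "proximal neck > 10mm in length, <= 32mm in diameter, and angulated no more than 80 degrees". The anatomic list in 2.0(5) sets the same three limits and ends: "angulated no more than 80 degrees relative to the long axis of the aneurysm".

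Section 3.1.0 says how the lists are used: "Patients will be considered anatomically suitable if they fulfill all of the appropriate" anatomic inclusion criteria. Patients must meet both the general and the anatomic criteria to enrol.

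**The concern.** The risk section identifies a group of patients whom the protocol thinks it wise not to treat, and the eligibility lists then let them in. An investigator who follows the lists to the letter would enrol a patient whom section 4.1.1.7 advises against enrolling.

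What is at stake is mainly patient safety. Section 4.1.1.5 makes balloon seating of the proximal stent a routine step. Appendix I (step 44) prescribes the order of ballooning at the neck so that soft material is less likely to be dislodged. Appendix H, on the Perth device, says that thrombus in the neck prevents fixation and can embolise when the balloon is used. The hazard and the manoeuvre that provokes it are both described, but nothing in the enrolment rules keeps them apart.

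There is also a point of interpretation. In a non-randomised study with no control group, the eligibility list defines the population to which the observed embolism and migration rates refer. Here a reader of the list and a reader of 4.1.1.7 would describe that population differently.

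**Working it through.** This is a comparison of texts. The plan gives no figure to reproduce, and no power or error rate is involved.

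**1. Search of the lists for a thrombus item.**

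| List | Where | Items | Items naming thrombus |
|---|---|---|---|
| General inclusion | 2.0(5), 3.1.1 | 6 | 0 |
| Anatomic inclusion | 2.0(5), 3.1.3 | 6 | 0 |
| Exclusion | 2.0(6), 3.1.2 | 7 | 0 |

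In total, 0 of 6 + 6 + 7 = 19 items. The anatomic items cover the proximal neck, iliac diameter, the inferior mesenteric artery, iliac angulation, the distal neck and the iliac implantation sites.

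**2. Search of the appendices for a rule.** Appendix A says thrombus calls for special consideration and lists its extent among the important features of the neck, but sets no limit. The Appendix B summary gives limits for neck diameter and length only.

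**3. Test case (illustrative).** Take a thrombus-lined neck 20 mm long and 30 mm wide, angulated by less than 80 degrees, in a patient who meets every other item. Length: 20 > 10. Diameter: 30 ≤ 32. Angulation: within the limit. It passes 3.1.3(a). It also passes the stricter 15 mm length in Appendix B. Under 3.1.0 the patient is anatomically suitable; under 4.1.1.7 it would be prudent to exclude the patient.

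**4. Can the risk be sized?** The source is the Perth series of 108 bifurcated grafts (Appendix H). Intervals are exact (Clopper-Pearson): the lower limit is the 2.5% point of Beta(x, n − x + 1) and the upper limit the 97.5% point of Beta(x + 1, n − x).

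- Peripheral emboli: 5/108 = 4.6% (95% CI 1.5 to 10.5%). None is classified by neck thrombus.
- Migration in a thrombus-lined neck: 1/108 = 0.9% (0.02 to 5.1%). This is one of the four migrations.

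A comparison needs the number of thrombus-lined necks treated, T, which is not given. For migration, the risk would be 1/T in lined necks and 3/(108 − T) in the rest, taking each case as having only the feature attributed to it. With assumed values of T:

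| T (assumed) | Lined necks | Other necks |
|---|---|---|
| 5 | 1/5 = 20.0% | 3/103 = 2.9% |
| 27 | 1/27 = 3.7% | 3/81 = 3.7% |
| 54 | 1/54 = 1.9% | 3/54 = 5.6% |

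The two are equal when 108 − T = 3T, that is T = 27. Without T, not even the direction of the difference is fixed by these data. For emboli, both T and the split of the five events are missing.

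**The case against.** The best defence is that the protocol means this to be a clinical judgement. The advice in 4.1.1.7 is hedged. The general list has its own item on suitable arterial anatomy, which would be redundant if the anatomic list were complete. Appendix A tells the investigator to weigh thrombus. The study runs at one centre, and the investigator reviews the imaging before consent (5.2.0), so different readings across sites are not an issue. Appendix F treats freedom from thrombus lining as a feature of the ideal neck and calls none of its cut-offs absolute. Appendix G calls its neck limits somewhat flexible and their effects cumulative.

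Part of this stands: the investigator can refuse such a patient, and nothing shows that thrombus-lined necks would in fact be treated. But the general item is undefined, and 3.1.0 ties anatomic suitability to the listed items. Section 3.1.0 also says that meeting any general item makes a patient high risk, so that item is a weak barrier. Appendices F and G concern another device family, and Appendix G also states that its current criteria exclude thrombus-lined necks. For the Perth device, Appendix H says its current criteria would exclude the migration cases, the thrombus-lined one included.

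A reader might go further and infer that 4.1.2.1 claims a safeguard this study lacks. The text does not settle that: the selection changes it mentions follow an account of the Perth experience and may be Perth's own. A reader might also want conical necks added to the point, but the body of the protocol gives no advice to exclude them, so there is no matching contradiction.

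**Conclusion.** The point holds as an inconsistency between the protocol's safety advice and its enrolment rules, and it should be corrected. The listed criteria admit patients with thrombus-lined necks whom 4.1.1.7 thinks it prudent to exclude, and only undefined discretion stands in the way.

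Its size in events is unknown. It is tempting to read the 4.6% embolism rate as the harm caused by the missing criterion, or to project it onto the 300 planned patients. The documents support neither. The five emboli are not tied to neck thrombus. The single migration that is tied to it came early in the Perth experience, and suprarenal placement of the proximal stent has since become routine (4.1.2.1). No endpoint, analysis or sample size is shown to be affected.

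The conclusion assumes that the eligibility lists in 2.0 and 3.1.1 to 3.1.3 are the complete enrolment rules. The text between 3.1.7 and 3.2.2 and the forms in Appendix E could not be read. If either holds a thrombus rule, the remedy is to repeat it in the lists.

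**What to change.** Add to the neck item in both 2.0(5) and 3.1.3(a): *no thrombus lining the proximal implantation site on the planning contrast CT or MR*. If the sponsor is willing to accept some thrombus, the tolerated extent should be stated in the same line, so that the criterion can be checked against the scan and does not become a second undefined judgement.

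This is a wording amendment. It needs no new imaging: Appendix A already has the extent of neck thrombus read after intravenous contrast, and both of its example protocols include a contrast run.

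The real cost is eligibility. Some patients who qualify now would not qualify under the new line, and the documents give no basis for estimating how many. These patients have an anticipated mortality above 10% with open repair, and 4.3.1 describes rupture as usually fatal for them, so each exclusion matters. That is a reason for the sponsor to consider the tolerated extent carefully, but 4.1.1.7 has already judged exclusion to be the prudent course.

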4.1.1.8 Systemic effects

The incidence of cardiopulmonary complications following any surgical procedure likely reflects the severity of the preexisting disease and the physiologic stress induced by surgery. The main advantage of an endovascular approach to aneurysm exclusion is the avoidance of the physiologic stress associated with abdominal operation, aortic cross clamping, and prolonged lower extremity ischemia. It is not surprising that endovascular aneurysm repair has been remarkably free of complications such as myocardial infarction, pneumonia, venous thrombosis, and prolonged mechanical ventilation, despite the severe nature of the cardiopulmonary disease in many of these patients⁹. The low complication rate relates to the limited femoral dissection, lower blood loss, and diminished amount of fluid sequestration.

4.1.1.9 Local effects

There were only four cases of wound related complications in the Perth series. This likely relates to the limited access required for the procedure. Additionally, in the absence of graft material in the femoral region, the severity of this complication is markedly decreased.

4.1.2. Performance related hazards

The properly functioning stent graft carries blood freely to the pelvis and legs, and prevents blood from entering the aneurysm cavity. To accomplish this, the stent-graft must have a stenosis free lumen, and the ends of the device must remain securely attached to the arteries proximal and distal to the aneurysm.

4.1.2.1 Proximal stent migration

This complication was seen in approximately 4% of the series described by the Perth group however, all occurred early in their experience. A retrospective analysis has improved our ability to predict which patients will suffer from migration. Looking specifically at the Perth experience, two migrations occurred in patients with an aortic implantation site measuring greater than 28 mm when an undersized stent-graft system was utilized. The third case occurred in a thrombus-lined neck, while the fourth case involved a conically shaped neck.

In addition to the necessary changes in the patient selection criteria, some changes were made to the stent-graft design and implantation methods. The proximal stent is now routinely placed in a supra-renal position. The healthier aortic wall affords better barb penetration and is more resistant to later dilation.

Appendix B contains detailed information regarding the benefits and safety of using supra-renal fixation device and other methods of ensuring aortic attachment.

